#### *PROMIS-Anxiety*

The analysis approach for this endpoint mirrors the above description for PROMIS-Anxiety

#### *PCS SF-6*

The change from study baseline to Day 90 in pain catastrophizing as measured by PCS SF-6 is a secondary endpoint. This analysis will compare the treatment groups, separately, to the control group using a MMRM analysis. The repeated measures are the change from baseline PCS SF-6 score obtained for Day 15, 30, 60, and 90, respectively. The model will include fixed categorical effects for treatment, week, treatment by week interaction, and the baseline PCS SF-6 score as a continuous covariate. We will employ the Stata *xtmixed* command with REML and an unstructured within-patient covariance structure for this model. We will evaluate the assumptions of this model, including normality, using residual and other diagnostic plots of model fit.

From this model, we will estimate least squares means, standard errors, treatment differences in least squares means, and 95% confidence intervals for each time point. Primary inference will be based on the treatment comparison of least squares means for Day 90 from this model, and a p-value will be presented for this time period only. The null hypothesis is that the mean difference in the primary endpoint between the experimental arms and the sham arm is zero, versus the alternative hypothesis that this difference is not zero.

The change from study baseline to Day 90 in weekly MME of prescribed medication is a secondary endpoint. Descriptive summary statistics will be presented for weekly MME of prescribed medication at two timepoints: baseline and Day 90. Analysis of this endpoint will compare the difference in weekly MME of prescribed medication between the treatment groups and control group at baseline and Day 90 using analysis of covariance (ANCOVA), adjusting for baseline MME. We will assess the assumptions underpinning the ANCOVA model graphically and will undertake appropriate transformation of the weekly average MME outcome as deemed appropriate. If no suitable transformations can be found, bootstrapped confidence intervals for the between-group differences in weekly MME will be produced. Both adjusted and unadjusted between-group comparisons will be presented with 95% confidence intervals.

---

#### 9.4.4 SAFETY ANALYSES

All safety analyses will be descriptive. No statistical testing will be performed.

---

#### 9.4.5 BASELINE DESCRIPTIVE STATISTICS

We will summarize demographic and baseline characteristics both by treatment group and overall. Any time-to-event counts will be measured from the day of randomization. Body Mass Index (BMI) will be calculated according to:  $BMI = \text{weight (kg)} / (\text{height (m)})^2$ . Age will be calculated according to:  $Age = (\text{date of event-birth date} + 1) / 365.25$ . Weekly average opioid dosage will be calculated as a 7-day average of daily maximum milligrams morphine equivalent (MME) as prescribed. Mean activity measures will be calculated as weekly averages (e.g. weekly steps, weekly sleep minutes). Activity classification (i.e.

sedentary versus light versus moderate, etc.) will be provided by FitBit and reported as such. Zip code will be matched to median income using census data as an aggregate measure of socio-economic status.

#### 9.4.6 PLANNED INTERIM ANALYSES

No formal interim analysis or interim statistical testing for treatment comparisons is planned.

#### 9.4.7 SUB-GROUP ANALYSES

Subgroup analyses are planned for the change from baseline in PROMIS-PI. An MMRM model will be used to test for treatment by subgroup interactions. Interactions with a significance level of less than 10% will be considered potentially important and flagged for further assessment. In general, the models will include fixed categorical effects for treatment, week, treatment by week interaction, subgroup, and treatment by subgroup interaction. The p-values of interaction terms will be presented, as well as the least squares means and 95% confidence intervals by treatment and subgroup classification factor. Descriptive statistics of the observed and change from baseline PROMIS-PI t-score will also be presented by treatment and week within each subgroup.

Subgroup analyses will be performed for the following subgroups:

- Dosage of VR (minutes per week)
- Previous experience with VR
- ITQ score
- Presence score
- Patient comorbidities
- History of spinal surgery
- Pain severity and duration
- Sociodemographics (i.e. age, sex, race, ethnicity, workers comp, marital status, education)
- Other treatments (see section 6.5)
- TAPS-1, TAPS-2
- Mood disturbances (e.g., current depressive disorder or not, severely depressed mood vs. non-depressed, etc.)
- Radicular vs. non-radicular back pain
- SSQ Cutoff (Score of >15)
- Treatment Expectation Question
- Perception of arm of study question
- Motion Sickness Propensity Survey

The primary MMRM models will be re-fit to include terms describing subgroups. The change from baseline PROMIS-PI score obtained at Day 30 will be compared between the treatment groups using MMRM analysis. The repeated measures are the change from baseline PROMIS-PI score obtained for Day 7, 15, 21, and 30, respectively. The model will include fixed categorical effects for treatment, week, treatment by week interaction, relevant subgroup, treatment by subgroup interaction, and the baseline PROMIS-PI score as a continuous covariate. The estimated least squares means and 95% confidence intervals on the treatment comparison for Day 7, 15, 21, and 30, will be presented in forest plots for each subgroup of relevance.

See Section 9.4.9 under exploratory analysis for more detail.

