## 1.2 SCHEMA

### 1.3 SCHEDULE OF ACTIVITIES (SOA)

Procedures	Pre-screening	Screening Week Day -8 to -2	Enrollment Day -1 to 0	Day 1 (+ 6 days)	Day 7 (+ 6 days)	Day 15 (+ 6 days)	Day 21 (+ 6 days)	Day 30 (+ 6 days)	Day 45 (+ 6 days)	Day 60 (+ 6 days)	Day 75 (+ 6 days)	Day 90 (+ 6 days)
Prospective patient identified (DEEP 6 or provider registry)	X											
Confirm eligibility and Informed Consent via telephone and REDCap	X											
Online Pain Intensity Journal (7 days)		X										X
Screening Week Online Baseline Survey (see below)		X										
Randomization			X									
Participant receives study intervention kit			X									
Technical onboarding call				X								
Intervention: Participant uses VR therapy program and wears Fitbit Charge 4 watch				X	-----							X
Online survey: NIH HEAL Minimum Dataset	X											X
Immersive Tendency Questionnaire (ITQ)  and Motion Sickness Propensity Survey 	X											
Treatment expectation question	X											
Simulator Sickness Questionnaire (SSQ)  and Presence Survey				X								
Online survey: Primary outcome: PROMIS® Pain Interference	X			X	X	X	X	X	X	X	X	X
Discontinuation of Treatment Questionnaire				X	X	X	X	X	X	X	X	X
PROMIS® Physical Function  , Anxiety  , Depression  , Sleep disturbance  ; Pain intensity/interference with Enjoyment of life/interference with General activity (PEG)  , PCS-6 	X				X		X	X		X	X	X
EMR data: Charlson Comorbidity Index  , CURES and EMR: Prescription Data	X											X
Perceived study arm question, treatments in the last 90 days question												X
Online survey: PHQ-2, GAD-2, PGIC, TAPS [1/2]	X											X
Remote technical support				X	-----							X
End of study procedure question												X

Procedures	Pre-screening	Screening Week Day -8 to -2	Enrollment Day -1 to 0	Day 1 (+ 6 days)	Day 7 (+ 6 days)	Day 15 (+ 6 days)	Day 21 (+ 6 days)	Day 30 (+ 6 days)	Day 45 (+ 6 days)	Day 60 (+ 6 days)	Day 75 (+ 6 days)	Day 90 (+ 6 days)
Event Assessment: AE, SAE and UP review and reporting				X	X	X	X	X	X	X	X	X

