## 9.2 SAMPLE SIZE DETERMINATION

### Sample Size calculations

The primary goal of this aim is to test the efficacy of immersive VR in improving perceived pain. The trial will be a success if there is statistical evidence that either immersive VR group is better than control or sham VR. Preliminary studies showed that the PROMIS pain interference scale has a SD of 10. Assuming that the SD at baseline ( $SD_0$ ) and at 30 days ( $SD_1$ ) are similar and equal to 10 for this population, the variance for the difference in PROMIS from baseline to 30 days after intervention is  $Var_{diff} = SD_0^2 + SD_1^2 - 2\rho SD_0 SD_1$ , where  $\rho$  is the correlation coefficient between measurements at baseline and 30 days. A conservative estimate of this variance is achieved when  $\rho = 0$ . Therefore, the estimate  $SD_{diff} = (10^2 + 10^2)^{0.5} = 14.14$ . Let  $m_c$ ,  $mv_1$ , and  $mv_2$  be the mean change in PROMIS score from baseline to 30 days for the control, VR1, and VR2 groups, respectively.

We estimate power by simulating 10000 trial replicates and testing the null hypothesis that  $H_0: m_c = mv_1 = mv_2$  versus the alternative hypothesis that  $H_1: m_c \neq mv_1$  or  $m_c \neq mv_2$ . To maintain the familywise error rate at 0.05, a two-sample t-test is used to compare the control arm to each VR arm and the test is declared statistically significant if the p-value of the two-sided test is less than 0.025. Under the alternative hypothesis that  $|m_c - mv_1| = |m_c - mv_2| = 5$ , data from 120 patients in each of the three arms achieve 83% power to detect a clinically meaningful effect 5 units in the PROMIS score. The actual type I error rate is 0.049. For the secondary outcome of comparison between the two VR arms, we test the null hypothesis that  $H_0: mv_1 = mv_2$  versus the alternative hypothesis that  $H_1: mv_1 \neq mv_2$  at the two-sided 0.05 level of significance if there is statistical evidence that both VR arms are better than control. Using the same assumptions as above and simulating 10000 trial replicates, then if both VR arms are better than the control arm, we can achieve 71.4% power to detect 5 units in PROMIS score between the two VR arms. This power was derived under the alternative hypothesis  $|m_c - mv_1| = 5$  and  $|mv_1 - mv_2| = 5$ . The actual type I error rate for this conditional test is 0.02.

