
To assess the efficacy of Skills-Based and Distraction VR via patients' global impression of change (PGIC). The objective will be considered achieved if there is statistical evidence of higher rates of self-reported improvement in either VR group compared to control (sham) VR.
	
The overall effect of treatment from study baseline to Day 90 as measured by the PGIC is an exploratory endpoint. This scale measures self-reported belief regarding efficacy of treatment. A favorable response of 5-7 on the PGIC indicates significant improvement occurred over the course of the study. We will test for a statistically significant difference in PGIC responses between either VR group and control (sham) VR.

To assess the efficacy of Skills-Based and Distraction VR in improving measures of physical activity from baseline to Day 90. The objective will be considered achieved if there is statistical evidence of measured improvement in either VR group compared to control (sham) VR.
	
The change from study baseline to Day 90 in weekly steps as measured by Fitbit is an exploratory endpoint. Change in steps will also be examined for interaction effects on the primary outcome.

To assess the effect of presence on the efficacy of Skills-Based and Distraction VR in improving measures of pain interference from baseline to Day 30.
	
The effect of presence - as measured by a custom, 6-item survey - on the efficacy of VR treatment for pain is an exploratory endpoint. Scores on the survey at Day 1 will be examined for interaction effects on the primary outcome.

To assess the effect of Immersive Tendencies on the efficacy of Skills-Based and Distraction VR in improving measures of pain interference from baseline to Day 30.
	
The effect of immersive tendencies - as measured by the ITQ - on the efficacy of VR treatment for pain is an exploratory endpoint. Scores on the ITQ at baseline will be examined for interaction effects on the primary outcome.

To assess the effect of dose on the efficacy of Skills-Based and Distraction VR in improving measures of pain interference from baseline to Day 30.
	
The effect of dose - as measured by minutes spent accessing therapeutic content on the VR device - on the efficacy of VR treatment for pain is an exploratory endpoint. Minutes spent accessing therapeutic content will be examined for interaction effects on the primary outcome.

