#### 4.6.3 Subgroup Analyses

Subgroup analyses are planned for the change from baseline in PROMIS-PI. An MMRM model will be used to test for treatment by subgroup interactions. Interactions with a significance level of less than 10% will be considered potentially important and flagged for further assessment. In general, the models will include fixed categorical effects for treatment, week, treatment by week interaction, subgroup, and treatment by subgroup interaction. The p-values of interaction terms will be presented, as well as the least squares means and 95% confidence intervals by treatment and subgroup classification factor. Descriptive statistics of the observed and change from baseline PROMIS-PI t-score will also be presented by treatment and week within each subgroup.

Subgroup analyses will be performed for the following subgroups:

- Dosage of VR (minutes per week)
- Previous experience with VR
- ITQ cutoff score
- Presence cutoff score
- Patient comorbidities
- History of spinal surgery
- Pain severity and duration cutoffs
- Socio-demographics (i.e. age, sex, race, ethnicity, marital status, zip code)
- Other Medications
- TAPS-1, TAPS-2

The primary MMRM models will be refit to include terms describing subgroups. The change from baseline PROMIS-PI score obtained for Day 30 will be compared between the treatment groups using MMRM analysis. The repeated measures are the change from baseline PROMIS-PI score obtained for Day 7, 15, 21, and 30, respectively. The model will include fixed categorical effects for treatment, week, treatment by week interaction, relevant subgroup, treatment by subgroup interaction, and the baseline PROMIS-PI score as a continuous covariate. The estimated least squares means and 95% confidence intervals on the treatment comparison for Day 7, 15, 21, and 30 will be presented in forest plots for each subgroup of relevance.

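### Four planned effect modifiers are measured after randomisation, so their interaction tests and subgroup effects can be biased and cannot be read as effect modification

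*Protocol*

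**What the plan says.** Protocol 9.4.7 refits the primary MMRM with a subgroup term and a treatment-by-subgroup term. It flags interactions significant below 10% and shows subgroup treatment comparisons in forest plots. Its 16 entries mix factors known before randomisation with VR minutes per week, presence score, SSQ above 15 and "Perception of arm of study question".

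SAP 4.6.3 (Subgroup Analyses) has a shorter list. It includes VR use, entered as "Dosage of VR (minutes per week", and a presence cutoff, but neither SSQ nor perceived arm. SAP 3.2 (Study Objectives and Endpoints) states the purpose for both. On use: "Minutes spent accessing therapeutic content will be examined for interaction effects on the primary outcome". On presence: "Scores on the survey at Day 1 will be examined for interaction effects on the primary outcome".

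The Schedule of Activities (Protocol 1.3) places randomisation at Day -1 to 0 and SSQ and presence at Day 1. The row "Perceived study arm question, treatments in the last 90 days question" is marked at Day 90 only. Protocol 9.4.1 defines baseline as the screening week. Neither document separates baseline from later subgroup variables, defines a window for VR minutes, adds a caveat, or names a method suited to post-randomisation variables.

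**The concern.** A subgroup comparison keeps the protection of randomisation only if membership was fixed before assignment. These four variables can respond to the assigned program. Presence is what the sham was built to remove (Protocol 4.1 and 6.1.1). Minutes can respond to pain, because participants may repeat sessions when in pain (4.3) and use the program as needed (6.1.2). The arm guess comes 60 days after the outcome it is supposed to modify, so improvement may shape the guess.

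Patients in the high-use or high-presence stratum may therefore differ in kind between arms. Dose and presence are named tertiary objectives (Protocol 1.1), and Protocol 2.2 asks whether usage patterns predict better response. A flagged interaction could be reported as a dose or presence effect where none exists, and subgroup effects in the forest plots could be too small.

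**Working it through.** **1. Timing, from Protocol 1.3**

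| Variable | Measured | Listed in |
|---|---|---|
| VR minutes per week | after the device is in use; no window given | Protocol 9.4.7, SAP 3.2 and 4.6.3 |
| Presence | Day 1 | Protocol 9.4.7, SAP 3.2 and 4.6.3 |
| SSQ above 15 | Day 1 | Protocol 9.4.7 only |
| Perceived arm | Day 90 only | Protocol 9.4.7 only |

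All four follow randomisation, and the last also follows the Day 30 outcome. ITQ, treatment expectation and motion-sickness propensity are collected beforehand and are sound. TAPS is collected at baseline and at the end of follow-up. Other treatments are covered by a Day 90 question about the preceding 90 days. The subgroup list does not say which time point it uses for these two.

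**2. The plan's own power figure (context only)**

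Inputs from Protocol 9.2: "Preliminary studies showed that the PROMIS pain interference scale has a SD of 10"; SD of change 14.14; effect 5; and "the test is declared statistically significant if the p-value of the two-sided test is less than 0.025". SE = 14.14 × √(2/120) = 1.825, and 5/1.825 = 2.74. Power per comparison is Φ(2.74 − 2.24) ≈ 69%. Simulating both tests against the shared sham arm gives 83.4% for at least one success, which agrees with "data from 120 patients in each of the three arms achieve 83% power". Nothing below changes this.

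**3. Link to relief differs by arm: spurious interaction**

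Assumed model: one VR arm against sham, 120 per arm; relief = 5 × arm + N(0, 10²); use = k × relief/10 + N(0, 1). The effect is 5 for everyone, so there is no true modification. Within an arm:

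- slope of relief on use: b = 10k/(1 + k²)
- variance of that slope: (100/120)/(1 + k²)²

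For k = 0.3 (VR) and 0 (sham): b = 3/1.09 = 2.75 and 0. SE = √(0.701 + 0.833) = 1.239, so z = 2.22. The chance of a flag at 10% is Φ(2.22 − 1.645) ≈ 72%.

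For k = 0.5 and 0.2: b = 4.00 and 1.92, a difference of 2.08. SE = √(0.533 + 0.770) = 1.142, so z = 1.82. The chance of a flag is Φ(0.17) ≈ 57%.

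Simulated flag rates:

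| k, VR vs sham | Continuous use | Median split |
|---|---|---|
| 0.3 vs 0 | 72% | 56% |
| 0.5 vs 0.2 | 55% | 48% |
| 0.3 vs 0.2 | 16% | – |
| 0.5 vs 0.4 | 13% | – |
| 0.3 vs 0.3, or 0.5 vs 0.5 | 10% | – |

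The median-split column is closer to the categorical subgroup terms in the plan. With SD 14.14 in place of 10, the 0.3 vs 0 case rises to 91% (continuous) and 78% (split).

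**4. Link to relief equal in both arms: attenuation**

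For a median split, the effect within strata is about 5 − (2/π) × b × Δ. Here b is the within-arm slope of the outcome on the splitting variable, Δ is the arm difference in that variable, and 2/π = 0.637.

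- *Arm guess.* Assume the guess follows Day 90 improvement plus noise of SD 5 or 10, that the Day 30/Day 90 correlation is 0.5, and that the effect is 5 at both days, so Δ = 5. Then b = 50/125 = 0.40 or 50/200 = 0.25. The effect becomes 5 − 0.637 × 0.40 × 5 = 3.7, or 5 − 0.637 × 0.25 × 5 = 4.2. Simulations give 3.7 to 4.3 in both strata, with about 10% of interactions flagged.
- *Arm also shifts the level.* Take k = 0.5 in both arms and let assignment raise use by a further 1 unit. Then b = 4, Δ = 0.25 + 1 = 1.25, and the effect becomes 5 − 0.637 × 4 × 1.25 = 1.8.

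These checks use a single time point and no baseline covariate, which is simpler than the planned MMRM. Presence and SSQ were not simulated separately; the same two mechanisms apply to them.

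**The case against.** The strongest reply is that measurement after randomisation does not by itself distort an interaction test. That is correct. With equal slopes the test holds its level, and small slope gaps add little (13% to 16%). A reader might infer that all these interactions are biased, or that about 72% of trials like this one would raise a false flag. The documents support neither reading. They give no slope for any of the four variables and do not establish that use follows relief differently by arm. Protocol 6.1.2 gives all arms the same instruction through the Day 30 window, and as-needed use makes dependence possible, not certain. A reader might also infer that the arm guess must create a false interaction. With an equal link it does not; it shrinks both stratum effects.

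The second reply is limited consequence. The work is labelled exploratory, a flag leads only to further assessment, exploratory tests sit outside the gatekeeping (SAP 6.3), and only 4 of 16 entries are named. This lowers the importance of the point but does not answer it. The exploratory label warns of chance findings, whereas this bias is systematic and a larger sample does not remove it. The attenuation case also stands against the first reply, because the plan reports subgroup effects as well as interaction p-values.

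**Conclusion.** The point holds with the wording *can be biased*. The timing facts are certain, and neither document addresses them. Under unequal links the interaction test can flag about half to three-quarters of trials with no true modification, for the larger slope gaps assumed here. Under equal links it stays near 10%, but a true effect of 5 can appear as about 3.7–4.3, or about 1.8 if the arm also moves the variable strongly. In neither case can the output be read as effect modification.

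The sizes depend on assumed slopes, noise, shift and a Day 30/Day 90 correlation of 0.5. They show what is possible and do not forecast this trial. It would be wrong to infer that the main result is compromised: the primary and secondary randomised comparisons, the sample size and the error control do not use these variables. The change should be made, but its importance is limited to the exploratory objectives.

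**What to change.** - **Protocol 9.4.7:** restrict treatment-by-subgroup interaction tests and forest plots to variables measured before randomisation. State that TAPS and other treatments enter at their baseline values.
- **SAP 3.2 and 4.6.3 (Subgroup Analyses):** make the same change for VR minutes and presence, and specify baseline values for the TAPS and medication entries. SSQ and perceived arm are not listed there and need no edit.
- **Reporting:** present VR minutes, presence and SSQ as within-arm associations and perceived arm as a blinding check, all labelled exploratory and non-randomised. State the window over which minutes are counted.

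This needs no new data and no change in sample size. The cost is that the tertiary dose and presence objectives (Protocol 1.1, SAP 3.2) must be reworded and reported as associations. If a mediation analysis is wanted instead, it needs its own stated assumptions and method, which the plan does not contain.

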#### 9.4.8 TABULATION OF INDIVIDUAL PARTICIPANT DATA

We will tabulate individual participant data according to the Clinical Data Interchange Standards Consortium (CDISC) Study Data Tabulation Model (SDTM) as specified by the Data Integration, Algorithm Development and Operations Management Center (DAC).

#### 9.4.9 EXPLORATORY OUTCOMES

A few exploratory hypotheses have been considered:

Exploratory Outcome: Global impression of change with pain treatment using PGIC

Question: Which intervention is associated with patient's perceived change in condition due to treatment?

Dependent variable: patient's perceived change in condition as assessed by PGIC

Comparisons: Superiority for both of the following (1) Distraction VR therapy vs. sham VR therapy; (2) skills-based VR therapy vs. sham VR therapy, if there is a statistically significant difference in Skills based VR vs Sham VR then a third test will be completed (3) Skills-based VR therapy vs Distraction VR therapy

Exploratory Outcome: Quality of sleep over time by biometric data on Fitbit Charge 4 (total minutes asleep and sleep efficiency per night)

Hypothesis: Skills-based VR will lead to a greater improvement in sleep quality than distraction based VR or Sham VR.

Comparisons: Superiority for both of the following (1) Distraction VR therapy vs. sham VR therapy; (2) skills-based VR therapy vs. sham VR therapy, if there is a statistically significant difference in Skills based VR vs Sham VR then a third test will be completed (3) Skills-based VR therapy vs Distraction VR therapy

Exploratory Outcome: Depression over time as measured by PROMIS Depression (version 4)

Hypothesis: Skills-based VR will lead to a greater improvement in PROMIS Depression than distraction-based VR or Sham VR.

Comparisons: Superiority for both of the following (1) Distraction VR therapy vs. sham VR therapy; (2) skills-based VR therapy vs. sham VR therapy, if there is a statistically significant difference in Skills based VR vs Sham VR then a third test will be completed (3) Skills-based VR therapy vs Distraction VR therapy

Exploratory Outcome: Increased physical function over time as measured by total steps using biometric data

Hypothesis: Skills-based VR will lead to a greater improvement in physical activity than distraction-based VR or Sham VR.

Comparisons: Superiority for both of the following (1) Distraction VR therapy vs. sham VR therapy; (2) skills-based VR therapy vs. sham VR therapy, if there is a statistically significant difference in Skills based VR vs Sham VR then a third test will be completed (3) Skills-based VR therapy vs Distraction VR therapy

Exploratory Outcome: Improvement in physical function as measured by PROMIS physical function (version 6b)

Hypothesis: Skills-based VR will lead to a greater improvement in physical activity than distraction-based VR or Sham VR.

Comparisons: Superiority for both of the following (1) Distraction VR therapy vs. sham VR therapy; (2) skills-based VR therapy vs. sham VR therapy, if there is a statistically significant difference in Skills based VR vs Sham VR then a third test will be completed (3) Skills-based VR therapy vs Distraction VR therapy  
See Section 4.6.3 of the SAP for details on the assessment of each the above outcomes.

